Participants assigned to intervention arm, peers and interventionists of the study will be interviewed at mid-point of the study and end of the study to provide their feedback on the STOMP intervention. These interviews will be audio-recorded and later transcribed using third party. Participants will be compensated \$50 for each of the qualitative interviews.

e) COMPARISON CONDITION

The comparison group will receive “treatment as usual” as described above. The comparison group will also be provided with the intervention manual, however, no additional treatment will be provided to participants allocated to the control group.

Assessments

The comparison group participants will complete the post-intervention (0-month) follow-up at the same timing of the intervention group (12 - 16 weeks) after the 1st intervention session., and then will complete the outcome assessments (3,6,9,12) as the intervention group as described above including the baseline and the 12-month viral load assessments, and the important medical event screening at post-intervention. We will continue to conduct assessments every six months until the end of the study for all participants who complete the baseline assessment by the beginning of Year 3. Participants who completed the baseline assessment by April 30, 2021 will continue to

receive outcome assessments until April 2023 for a maximum of 41 months or 3 years. These assessments may be conducted by phone, if necessary, or in person.

We will also investigate the intervention's impact on use of prescribed and non-prescribed opioids. Study staff will ask at each outcome assessment (3,6,9,12) the name of the participants' pharmacies along with the list of their current medications and dosage. Study staff will print out the medication lists and review it against the Opioid Medication Resource to identify the prescribed opioids. With written consent and a signed release of information from participants, a study staff member will contact the participants' pharmacy (or pharmacies) at the 12-month assessment to verify the self-reported information provided by the participants in the prior assessments. The data will be added into an excel spreadsheet for collection and analysis. Participants will receive up to 3 reminder calls at about a week and 48 hours prior to the next outcome assessment.

f) PEER INTERVENTIONISTS

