As a peer interventionist, they will lead the intervention groups. Having peers facilitate the intervention groups fosters relationships with the participants since both groups share similar experiences. Peer interventionists will be compensated \$500 for the initial training time and an additional \$1,500 per the intervention block.

Each participating site will employ up to three peer interventionists for the group sessions. Peers should be living with HIV and be good pain self-managers. They must be mature, personable, highly responsible, with good communication skills and be able to follow rules of confidentiality. Potential peers may be identified by the

healthcare team or self-referrals and will be interviewed by research staff. They will not have contact with external institutions until officially hired.

During each 16 week cycle, one peer will serve as the lead interventionist and will co-facilitate (along with the staff interventionist) a group of ten participants; the other two (at sites when more than one peer is hired) will serve as first and second backup. The lead and first (active) back-up should attend all 6 group sessions. The second back-up will be utilized in the event a peer decides to drop out of the study. Determination of which two peers to start the intervention will be based on their scheduling preference. Research staff will conduct periodic check-ins to the active and (inactive) back-up to ensure he/she remains engaged in the study.

Peers will be responsible for the following activities.

Lead peer

1. Complete IRB and Good Clinical Practice certification
2. Participate in a 2 day STOMP training on pain self-management on an annual basis
3. Participate in 2 – 5 individual training sessions and 2 mock group sessions with staff intervention prior to start of intervention
4. Co-lead 6 one hour group sessions over a 12 - 16 week period for three years (arrive 30 minutes before and stay 30 minutes after) and attend weekly debriefing calls
5. Conduct reminder calls for the group sessions and provide phone-based peer support to intervention participants (as needed, during scheduled time)
6. Lead peer interventionist could work approximately 2 - 5 hours per week during each intervention cycle

First Backup peer

1. Complete IRB and Good Clinical Practice certification

2. Participate in a 2 day STOMP training on pain self-management on an annual basis

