We will use a structured fidelity assessment tool developed by the study PI and psychologist consultant [name]. To assess one-on-one session fidelity across interventionists, time, and sites, we will audio record sessions. Initially, we will listen to and rate all one-on-one sessions. Once an interventionist completes five consecutive sessions with 80% fidelity, we will "certify" the interventionist as having the competence necessary to continue to conduct the intervention. Thereafter, a blinded assessor with intervention delivery experience trained by [name] will review a 10% random sample. We will also provide ongoing supervision to prevent interventionist drift. We will monitor treatment receipt by using a checklist, which will capture whether

participants have used their tracking logs (which will be photocopied at each session by the staff interventionists). Given the less structured format of the group sessions, they will be assessed for knowledge sharing between the peers and participants and among participants, reflection on one-on-one session content, and fostering social support.

h) COLLECTION OF COST DATA

Each site will be responsible for tracking the following items in real-time: up-front training hours, cost of snacks, travel vouchers and participant manuals. Individual and group sessions will be tracked using the audio-record capability.

i) COLLECTION OF CNICS DATA

Center for AIDS Research Network of Integrated Clinical Systems (CNICS) Data:
CNICS data will be collected from abstractions from site medical record databases in collaboration with the CNICS data collection and patient reported outcomes infrastructure. Clinical and medical history data will include HIV viral load, CD4+ T-cell counts, co-morbid conditions, HIV primary care visit adherence, and medications. HIV primary care visit adherence will be extracted on all HIV care visits from the date of enrollment until the end of the study. Data from CNICS Patient Reported Outcomes (PRO) questionnaires including assessments of pain will be identified by study code and managed in accordance with CNICS electronic storage and data transfer guidelines.

j) TRACKING OF STUDY PATIENTS

Study staff will use the study's RedCap database to capture reminder calls, study visits, assessments, and intervention activities. Study staff will use excel logs to capture

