[name]	Data Analyst	University of Alabama at Birmingham
[name]	Qualitative Interviewer	University of Alabama at Birmingham
TBD	Research Staff	University of North Carolina at Chapel Hill
[name]	Data Manager UNC	University of North Carolina at Chapel Hill
[name]	Project Manager	University of Pittsburgh

Statistical Analysis Plan

Study Design & Objectives. Our overall objective is to evaluate a novel theory-based PSM intervention, “Skills TO Manage Pain” (STOMP) developed for people with HIV (PWH). The design of the proposed study is a multicenter parallel-group individually randomized group clinical trial. The primary outcome is to evaluate the efficacy of STOMP, a theory-based intervention tailored to improving chronic pain in PWH immediately post intervention. The secondary outcomes are to investigate additional pain outcomes and proximal outcomes as potential mediators of STOMP’s impact on chronic pain immediately post intervention and at 3 months.

The study will be conducted at 2 institutions in the United States (University of Alabama at Birmingham (UAB) and University of North Carolina at Chapel Hill (UNC)), and we will enroll adult patients, ages >18 years of age, consented to participate in the CFAR Network of Integrated Clinical Systems (CNICS), English-speaking, having at least moderate chronic pain, ability and willingness to attend the group sessions at the date/time specified, and no plans for major surgery during the study period that would interfere with study procedures.

The primary hypothesis is STOMP will decrease pain severity and improve function (as measured by BPI-total) in PWH. To test this hypothesis, we propose a two-arm randomized trial of STOMP vs. an enhanced usual care comparison condition. Our primary outcome will be Brief Pain Inventory (BPI)-Total score and will be measured at baseline and immediately post-intervention (~12 weeks after first intervention session). Our secondary outcomes will be changes in additional pain scales (PEG and BPI subscales of BPI-pain severity and BPI-interference), pain self-efficacy questionnaire (PSEQ), Patient Health Questionnaire (PHQ-8), and pain catastrophizing scale (PCS) between groups immediately post intervention. We will examine sustained differences in primary and secondary outcomes at 3 months post intervention.

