Sample Size Calculation. Our primary outcome is the BPI-Total score as described above. Given that 20 participants progress through the study at a time, our total sample size should be divisible by 20. A sample size of 210 will provide 85% power to detect a difference of 1 on a 10 point scale with at standard deviation of 2.4 assuming a two-sample t-test with equal variance. The IMMPACT guidelines suggest that a change of 1 on the BPI is a minimum clinically significant difference. Additionally, the difference we found in our pilot trial was 1 (SD=2.4). Therefore, a sample size of 210 is sufficient to detect this effect size. To become divisible by 20 and allow for 25% dropout (slightly more than in the pilot trial) we will recruit 280 participants. With our anticipated sample size, we will be able to estimate a margin-of-error of 1.5 percentage points for 95% intervals. For secondary outcomes, we can detect an effect size of 0.4, a medium effect, for continuous measures and a difference of proportions between 7.5% and 17% for binary measures, each with 85% power.

Interim & Final Analyses. We will not have any planned interim looks for stopping for efficacy, although safety and tolerability data will be monitored by the study DSMB at each meeting. The final analyses will be conducted once study follow-up is complete, after all data is

cleaned, and once the study database is locked. We anticipate database lock will happen by February 2024 with completion of primary analyses occurring by March of the same year.

Analysis Sets. The full analysis set will be based on an intention-to-treat (ITT) analysis with a per-protocol (PP) sensitivity analyses. The ITT analysis set will comprise all participants who have been randomized to either study arm, regardless of length of follow-up or actual intervention received.

Endpoint and Covariates

Our primary outcome will be the Brief Pain Inventory (BPI)-Total score, a commonly used composite measure of pain severity and the impact of pain on an individual's function. The BPI asks 11 questions about pain severity (pain at its worst, least, average, and right now) and the interference of pain in several aspects of patients' lives (activity, mood, walking ability, work, relations with other people, sleep, and enjoyment of life) on a scale of 0 (no pain/does not interfere) to 10 (pain as bad as you imagine/completely interferes). The BPI-Total score is the average score across all 11 questions.

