There were no covariates included in our models, only time and treatment group indicator. We used linear mixed effects models which do not require adjustment for baseline as a fixed effect as it is included as an outcome. This allows for estimation of treatment effects at all follow-up times that takes into account any baseline differences between groups.

Handling of Missing Values. As a preventive measure, we will make every attempt to document all reasons for missing data. In addition, baseline characteristics will be compared between participants who do and do not withdraw from the study as a way to assess the impact of missing information and attrition. We will also compare the rates of lost-to-follow-up (LTF) between study arms.

Our general assumption will be that missing data is of the Missing at Random (MAR) mechanism. In this case, the use of linear mixed models for the primary analysis will be sufficient in reducing the impact that missing data has on biasing the primary results. Additionally, we will conduct a sensitivity analysis using multiple imputation via chained equations (MICE) to see how robust the overall inferences are.

Statistical Analyses.

The primary outcome – BPI-Total score – and the other secondary outcomes will be assessed as continuous variables. Linear mixed effects models will be performed to test differences between intervention and control conditions at the immediate post intervention and at 3 months. Models will include random effects for participant and therapy group. Therapy group is an identifier of the group of 20 that were randomized to create a STOMP group of 10. Fixed effects will be STOMP indicator, time and STOMP by time interaction. The primary hypothesis will be tested using the least squared means of each group at each time. We will check distributional

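### The therapy-group random effect is tied to the cohort of 20, which spans both arms, so it does not carry STOMP-group clustering into the primary standard error, and the 85% power assumes no such clustering

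*Combined protocol and SAP*

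**What the plan says.** The SAP (Study Design & Objectives) describes a "multicenter parallel-group individually randomized group clinical trial", so the plan recognises that one arm is treated in groups. Under Statistical Analyses it states: "Models will include random effects for participant and therapy group". It then defines the second of these: "Therapy group is an identifier of the group of 20 that were randomized to create a STOMP group of 10". The fixed effects are arm, time and their interaction, and the test uses the least-squares means by arm and time. No covariance structure or degrees-of-freedom method is given. Endpoint and Covariates adds that the models "do not require adjustment for baseline as a fixed effect as it is included as an outcome", so baseline rows are part of the response. The 30% responder model reuses the primary model's random components.

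On delivery, the protocol (III f, Peer Interventionists) says the lead peer "will co-facilitate (along with the staff interventionist) a group of ten participants". For usual care (III e, Comparison Condition), apart from the manual, "no additional treatment will be provided to participants allocated to the control group". Of the group sessions, III g (Fidelity Assessments) says "they will be assessed for knowledge sharing between the peers and participants and among participants".

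On size, the SAP (Sample Size Calculation) says: "A sample size of 210 will provide 85% power to detect a difference of 1 on a 10 point scale". It uses an SD of 2.4 and a two-sample t-test, then goes from 210 to 280 for 25% dropout. No ICC or design effect appears.

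**The concern.** Correlation caused by the sessions can arise only among people who attend them, and only after baseline. Sessions that aim at shared knowledge and mutual support make some correlation plausible. The model's group term is attached to a different unit: the cohort, with its usual-care members included and its baseline rows covered. A term common to both arms removes variation between cohorts, which is useful, but it leaves the between-arm comparison as if STOMP participants were independent of one another.

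At stake are the standard error, confidence interval and p-value of the primary test. The error favours a positive finding. The secondary continuous outcomes and the responder analysis share the same structure.

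**Working it through.** **Inputs from the documents.** 1:1 allocation; cohorts of 20, so 280/20 = 14 cohorts and 14 STOMP groups of 10; 210 evaluable (105 per arm); difference 1; SD 2.4 (variance 5.76); 25% dropout, hence 105/14 = 7.5 evaluable per STOMP group.

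**Assumptions.** Two-sided alpha 0.05 (not stated, but it reproduces the stated power); ICC 0 to 0.10 (not stated).

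**The plan's own figure.** A t-test with 105 per arm, difference 1 and SD 2.4 has power 85.2% (normal approximation 85.5%), and 210/0.75 = 280. The stated figures reproduce under independence, and dropout uses up the whole step from 210 to 280.

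**Why the term cancels.** Let c be the effect of a cohort and g the effect of its STOMP group. The within-cohort difference between arms contains c − c = 0, but it keeps g. Cancellation is exact with equal numbers per arm in each cohort and nearly so otherwise. A cohort-by-time effect is also common to both arms and cancels in the same way.

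**Closed form.** With total variance held at 5.76, the STOMP mean has variance

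ICC × 5.76/14 + (1 − ICC) × 5.76/105 = (5.76/105) × (1 + 6.5 × ICC).

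Adding 5.76/105 for usual care gives the true variance of the difference. Dividing by the variance under independence gives the SE ratio r = √((2 + 6.5 × ICC)/2). Type I error is 2 × (1 − Φ(1.96/r)), and power of a size-holding test is Φ(1/SE − 1.96).

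At ICC 0.05:
- Variance is 0.05486 × 1.325 + 0.05486 = 0.1275, so SE = 0.357.
- r = 1.078, so type I error is 2 × (1 − Φ(1.818)) = 6.9%.
- Power is Φ(2.800 − 1.96) = 80.0%.

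| ICC | True SE | r | Type I, closed form | Type I, simulated | Power, normal | Power, Satterthwaite df |
|---|---|---|---|---|---|---|
| 0 | 0.331 | 1.000 | 5.0% | 4.4% | 85.5% | 84.0% |
| 0.01 | 0.337 | 1.016 | 5.4% | 5.3% | 84.4% | 82.8% |
| 0.02 | 0.342 | 1.032 | 5.8% | 5.6% | 83.3% | 81.5% |
| 0.05 | 0.357 | 1.078 | 6.9% | 7.2% | 80.0% | 77.9% |
| 0.10 | 0.381 | 1.151 | 8.9% | 9.0% | 74.6% | 72.0% |

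The Satterthwaite column uses 13 degrees of freedom for the STOMP arm (14 groups).

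**Simulation of the planned model.** Set-up: 14 cohorts of 10 + 10, 7 or 8 evaluable per arm, dropouts contributing baseline only, three time points, within-person correlation 0.5 (assumed), group effect in STOMP follow-up rows only, REML, z-tests, 2000 runs per ICC (about ±1 point). The contrast is the least-squares-mean difference immediately post-intervention.
- The reported SE stays at 0.32 throughout, while the true SD of the estimate is 0.320, 0.326, 0.332, 0.349 and 0.368 across the five ICCs.
- The cohort term does not pick up the clustering: its median variance estimate is 0.009 and 0.030, against true STOMP-group variances of 0.288 and 0.576 (ICC 0.05 and 0.10).

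**Which structures work (simulated type I error).**

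| Random effects besides participant | ICC 0.05 | ICC 0.10 |
|---|---|---|
| Cohort of 20 (as planned) | 7.2% | 9.0% |
| Cohort + cohort-by-time | 7.2% | 9.1% |
| Cohort + arm-by-cohort, all rows | 6.3% | 8.3% |
| Cohort + arm-by-cohort, post-baseline rows | 4.8% | 5.4% |
| Cohort + STOMP group, post-baseline rows | 4.5% | 5.5% |

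The all-rows version fails because baseline is modelled as an outcome and carries no group effect.

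**Rejection rate at a true 1-point difference (simulated), ICC 0 to 0.10.** Planned model: 88.1, 87.4, 87.2, 85.9, 85.4%. Corrected model (last row above): 87.1, 86.1, 85.0, 82.2, 76.7%. Both start above the t-test figure because the mixed model also uses baseline data. The planned model's apparent power holds up only because its SE is too small.

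**The case against.** The strongest reply is that the harm depends on an ICC the documents do not supply. That stands. At 0.01 to 0.02 the inflation is under one percentage point and within simulation error. Half of the 12 sessions are individual, and missed sessions can be made up or joined by phone, which may dilute group correlation. These features argue for a smaller ICC, not for a model that requires it to be zero.

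Second, the t-test power figures overstate the shortfall for a mixed model. That is fair: on the simulated mixed-model basis, 85% survives up to ICC 0.02. Those simulations used z-tests, so small-sample degrees of freedom would lower them somewhat. With no dropout (140 per arm), power at ICC 0.05 and 0.10 would be 88.3% and 82.5%, so the shortfall depends on dropout as well.

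Third, the within-person correlation was fixed at 0.5. Varying it from 0.3 to 0.7 at ICC 0.05 leaves type I error at 7.0 to 7.2% for the follow-up mean contrast. If the contrast were change from baseline, it would range from 6.5% to 8.4%. The conclusion does not turn on this.

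Fourth, because the covariance structure is unstated, a random STOMP-by-time coefficient by therapy group might be intended, and that could carry the clustering. The text does not say so, and a plain intercept is the natural reading.

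Fifth, the SAP allows that some controls may cross over, so session-related correlation may not be confined strictly to the STOMP arm. This is minor.

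**Conclusion.** The concern holds. As defined, the therapy-group term follows the wrong unit and cannot bring STOMP-group clustering into the primary standard error. That follows from the definition and needs no ICC value. The size does: by the closed form the reported SE is about 2 to 3% too small at ICC 0.01 to 0.02, 7% at 0.05 and 13% at 0.10, with the type I errors tabulated above. At ICC 0 the planned test is sound.

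The stated 85% is arithmetically right for independent observations only. The figures rest on an assumed ICC range, two-sided alpha of 0.05, 7.5 evaluable participants per STOMP group and no correlation across groups. This should be fixed before the primary analysis is run, because it concerns the main inference and the correction is small.

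**What to change.** 1. Keep the random effect for the cohort of 20 as a block. It is the primary model's only term for shared cohort, period or site variation.
2. Add a random effect for the STOMP group of 10, acting only on STOMP participants' post-baseline observations. An arm-by-cohort effect limited to post-baseline rows also works; one that covers the baseline rows does not.
3. State the full covariance structure and the degrees-of-freedom method (Satterthwaite or Kenward-Roger).
4. Use the same random structure in the 30% responder model.
5. Restate power over an ICC range under one degrees-of-freedom convention, and say whether the lower power is accepted. By the normal approximation with 25% dropout, holding 85% would need about 276, 285, 294, 321 and 366 recruits at ICC 0, 0.01, 0.02, 0.05 and 0.10, before rounding up to a multiple of 20, against 280 planned. If recruitment is complete, this serves as disclosure.
6. Record as a limitation that peers or staff interventionists who serve several cycles could create correlation across groups, which the added term does not capture.

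**Cost.** SAP wording, one model statement and a revised power paragraph; no new data. The average 95% half-width grows from about 0.63 to 0.65, 0.68 and 0.73 points at ICC 0.02, 0.05 and 0.10 with normal quantiles, or roughly 0.67, 0.70 and 0.76 with Satterthwaite t quantiles (about 2.02 to 2.04). At ICC 0 the added term costs about 1 point of power (87.1% against 88.1% in simulation with z-tests). The combination of the added term with small-sample degrees of freedom was not simulated, so its exact cost should be checked when the SAP is revised.

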All participants in the intervention group will also receive a REDCAP assessment at baseline, post-intervention (0-month, after all sessions are completed), and then at 3, 6, 9 and 12 months post-intervention. The primary outcome will be at 3 months, and a 1-month window will be allowed after each timepoint for the patient to be contacted and assessed. An important medical event form will be administered to each participant at post-intervention (0-month) to screen for any unexpected medical incident, the severity of the event, its relation to the study, and medical follow-up. Viral load will also be

collected at baseline and at 12 months. At baseline, if a viral load from the prior 6 months is available in the medical record, that value will be recorded; otherwise, a viral load will be drawn. At 12 months, if a viral load in the prior 3 months is available in the medical record, that value will be recorded; otherwise, a viral load will be drawn. We will continue to conduct assessments every six months until the end of the study for all participants who complete the intervention by the beginning of Year 3. Participants who completed the baseline assessment by April 30, 2021 will continue to receive outcome assessments until April 2023 for a maximum of 41 months or 3 years. These assessments may be conducted by phone, if necessary, or in person. They will also participate in an audio-recorded in-person qualitative interview at the mid-point and end of the trial which will be transcribed using a third party company.

We will also investigate the intervention's impact on use of prescribed and non-prescribed opioids. Study staff will ask at each baseline and outcome assessment (0,3,6,9,12) the name of the participants' pharmacies along with the list of their current medications and dosage. Study staff will print out the medication lists and review it against the Opioid Medication Resource to identify the prescribed opioids. With written consent and a signed release of information from participants, a study staff member will contact the participants' pharmacy (or pharmacies) at the 12-month assessment to verify the self-reported information provided by the participants in the prior assessments. The data will be added into an excel spreadsheet for collection and analysis. Participants will receive up to 3 reminder calls at about a week and 48 hours prior to the next outcome assessment.

Qualitative interviews

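### The plan does not fix one visit for the primary BPI-Total test; if either visit can count, the false-positive rate is about 7–9%, not 5%

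*Combined protocol and SAP*

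**What the plan says.** Three places bear on when the primary hypothesis is tested, and they differ.

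- **SAP, Study Design & Objectives.** BPI-Total "will be measured at baseline and immediately post-intervention (~12 weeks after first intervention session"). The 3-month visit comes in afterwards: "We will examine sustained differences in primary and secondary outcomes at 3 months post intervention".
- **Protocol, section III(d), Assessments.** "The primary outcome will be at 3 months", counted from the end of the intervention. Section III(e) has the comparison arm follow the same schedule.
- **SAP, Statistical Analyses.** The mixed models are to "test differences between intervention and control conditions at the immediate post intervention and at 3 months", followed by "The primary hypothesis will be tested using the least squared means of each group at each time". No visit is singled out.

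The SAP lists six secondary scales: PEG, BPI severity, BPI interference, PSEQ, PHQ-8 and PCS. They are assessed immediately post-intervention and again at 3 months. A comparison of 30% responders on BPI-Total is added without a stated visit. On power, the SAP says "For secondary outcomes, we can detect an effect size of 0.4, a medium effect, for continuous measures", at 85%.

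The SAP gives no test-level alpha, testing order or multiplicity adjustment, and does not call these secondary results exploratory. The protocol uses that term only for the HIV outcomes.

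**The concern.** With one primary endpoint, the 5% error rate depends on knowing beforehand which single test decides the matter. Here each of the two visits has textual support as the primary one, and the sentence that governs the test covers both. An ineffective intervention would then have two chances to produce a positive primary result, and either could be defended from the documents.

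The SAP describes this as the first efficacy trial of STOMP, so readers will rely on a clear statement of which result was confirmatory. The secondary scales raise a related but separate question. The SAP treats proximal outcomes as possible mediators, so an isolated significant result on, say, PSEQ or PCS could be read as evidence of mechanism when nothing in the plan says how much weight it carries.

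**Working it through.** **1. Reproduce the plan's sample size, to find the implied alpha.** Inputs from SAP, Sample Size Calculation: difference 1, SD 2.4, power 85%, two-sample t-test. Allocation 1:1 is from the protocol's Randomization text.

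- n per arm = 2 × (1.960 + 1.036)² × 2.4² / 1² = 2 × 8.978 × 5.76 = 103.4, so 104 per arm (208 in total; the plan says 210).
- Power at 105 per arm: (1/2.4) × √(105/2) = 3.019; Φ(3.019 − 1.960) = 85.5%. The non-central t gives 85.2%.
- Recruitment: 210 / 0.75 = 280.

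The plan's figures reproduce with a two-sided 5% test. A one-sided 5% test would need only 166. Two-sided 5% is therefore the implied level for one test at one visit.

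**2. Type I error if either visit can support the primary claim.** With Z₁ and Z₂ the two visit statistics under no effect and ρ their correlation, the error is 1 − P(|Z₁| ≤ 1.96 and |Z₂| ≤ 1.96). The documents give no ρ, so a range is assumed.

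| ρ between visits | P(at least one significant) |
|---|---|
| 0 (independent) | 1 − 0.95² = 9.75% |
| 0.5 | 9.1% |
| 0.7 | 8.3% |
| 0.9 | 7.0% |

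If one visit alone decides, the error is 5%.

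**3. Cost of two ways to restore 5%, at 210 evaluable.**

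- Fixed sequence (named visit first at 5%, other visit only if the first is significant): the primary test keeps its 85%.
- Bonferroni split (2.5% per visit): about 78% power per visit, and 85% would need 248 evaluable.

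**4. Secondary scales.** Six scales at two visits make 12 tests at two-sided 5%. Correlated normal test statistics were simulated under no effect on any scale (400,000 draws; all correlations assumed).

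| Between-scale correlation | Between-visit correlation | P(at least one of 12) |
|---|---|---|
| 0.3 | 0.6 | 39% |
| 0.5 | 0.6 | 34% |
| 0.7 | 0.7 | 26% |

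Independence would give 1 − 0.95¹² = 46%. Six scales at one visit give about 16–24% for between-scale correlations of 0.7–0.3. The responder comparison is left out of these counts.

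**5. Secondary detectable effect.** At 105 per arm and two-sided 5% (non-central t), 0.4 SD has 82% power, and 85% power needs about 0.415 SD.

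**The case against.** The strongest reply is that the SAP does name one primary endpoint at one time. Its objectives section places BPI-Total immediately post-intervention and describes 3 months as a check on whether differences last. If that section governs, the primary error is 5%. The sentence about each time may only describe how contrasts are drawn from the model. Baseline is itself an outcome in that model, so a fully literal reading would include a baseline test, which is plainly not intended.

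This reply is fair, and it rules out saying that the plan definitely runs two primary tests. It does not close the matter. The protocol puts the primary outcome at 3 months, and no text says which document or section prevails.

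Other parts of the opposing case stand and limit the point:

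- A reader might infer that the chance of a falsely positive trial is far above 5%. The documents do not support that. Unadjusted secondary tests do not raise the error of the primary claim, and the primary excess is at most 4.75 percentage points.
- A reader might infer that a significant secondary result is more likely than not by chance. The figures of 26–39% are all below one half, and they count the 3-month look at each scale as a fresh claim.
- BPI severity and BPI interference are components of BPI-Total, so a common correlation as low as 0.3 is hard to defend and the upper figure is weakly supported.
- Testing responders at both visits is an inference from the shared model effects; the SAP does not state it.

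**Conclusion.** The point holds in limited form. The two SAP sections and the protocol do not agree on the primary visit. If significance at either visit can support the primary claim, the two-sided type I error is about 7–9% for between-visit correlations of 0.9–0.5, and 9.75% at most under independence. This rests on an assumed two-sided 5% level, which reproduces the plan's sample size, and on assumed correlations. If a single visit governs, the excess is zero, so this is an ambiguity to remove and not proof of an inflated primary test.

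Separately, the secondary scales have no multiplicity control and no label that would make control unnecessary. The 26–39% figure describes that family only, under its assumed correlations. The gap between 0.4 and 0.415 SD is a rounding matter and not an error in the design.

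**What to change.** 1. Reconcile the protocol's Assessments text with the SAP's Study Design & Objectives and Statistical Analyses sections so that all name the same primary visit, and state the test level (two-sided 5%).
2. Replace the wording on testing at each time with one test: the STOMP versus comparison contrast in BPI-Total at the named visit. Test BPI-Total at the other visit, also at 5%, only if the first is significant.
3. For the six secondary scales, either control them (for example Holm at the primary visit, after the primary test succeeds) or label them exploratory and report estimates with 95% confidence intervals. Labelling is enough if no confirmatory claim is intended. With Holm, the first-step detectable effect at 85% power and 210 evaluable is about 0.51 SD (alpha 0.05/6).
4. State the visit or visits for the responder comparison, and label it exploratory unless it has a place in the testing order.
5. Optionally, restate the unadjusted secondary detectable effect as about 0.415 SD, or its power at 0.4 SD as 82%.

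The cost is wording. The primary test keeps about 85% power at 210 evaluable, and recruitment stays at 280. One caution: the SAP's Endpoint and Covariates section describes the models partly in the past tense. The change should be dated against database lock and unblinding; if analysis had already begun, the testing order could not be presented as pre-specified.
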